Study Title: Feasibility of the Camp Power Up Program on Children's Body Weight and Quality of Life

NCT #: NCT03235440

Document date: September 1, 2020

We used SPSS to conduct paired t-tests to analyze any pre-to-posttest changes in health behaviors and psychosocial well-being outcomes. Cohen's d was computed as effect size to interpret the between time differences. Subsequently, we conducted repeated measure multivariate analyses of variance (RM-MANOVAs) to examine pre-to-posttest changes in health behaviors and psychosocial well-being outcomes by gender (boys vs. girls) and household income (\$50,000 as the split value). We further explored the pre-to-posttest changes in the outcomes (using gain scores: posttest – pretest data) by weight status (normal weight, overweight, obesity), but did not perform inferential statistical analysis due to the uneven sample sizes between the weight groups. Descriptive results including both raw and estimated marginal means were obtained to quantify and visualize group differences. Partial eta square (η^2) was reported as effect size from results from the RM-MANOVAs, while significance level was set to be $\alpha = 0.05$.

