The U.S. Preventive Services Task Force identifies behavioral treatment including dietary, physical activity, and behavioral counseling components as a viable option for pediatric obesity treatment,² yet a key challenge is how to implement these programs to maximize access and participation. Summer (between school years) represents an opportunity for intensive intervention to change health behaviors and help children to lose weight. During the summer months, children gain weight at a more rapid pace^{3,4} and spend more time engaged in sedentary behavior⁵ compared to the school year. The American Diabetes Association launched Camp Power Up as a summer week-long day camp for youth who are obese and/or at high risk for developing type 2 diabetes. The camp will focus on wellness education, nutrition, physical activity, and obesity prevention. The purpose of the proposed study is to examine effects of Camp Power Up on children's weight status and their psychosocial health.

Inclusion and Exclusion Criteria

Children must meet the following eligibility criteria to participate in the study:

- Aged 6 to 14 years
- Enrolled in the ADA Camp Power Up

Number of Subjects

We plan to enroll up to 62 participants total. A total of 12 participants were enrolled in summer 2017 and an additional 50 are anticipated for summer 2018.

Recruitment Methods

All children selected to participate in the ADA summer camp program will be asked to participate in this study. The ADA anticipated enrollment of approximately 50 children for the one week session each summer (summer 2017, summer 2018). Recruiting efforts include, but are not limited to the institution's email listserv, social media posts, and flyer drops.

Study Timelines

The enrollment and participant's participation in the study will last approximately one week (five daytime sessions). The primary analyses will be completed by January 1, 2018 for the summer 2017 camp. The primary analyses for the summer 2018 camp will be completed by January 1, 2019.

Study Endpoints

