AIM 1: Evaluate the effects of a one-week obesity prevention summer camp on children's weight, self-reported health behaviors, quality of life, mood and feelings, self-esteem, weight management efficacy, enjoyment of physical activity, and body image. Difference scores will be calculated between initial and final assessment, and effect sizes will be calculated using linear mixed models to determine clinical significance of weight-related and psychosocial changes throughout the program.

AIM 2: Examine the acceptance and feasibility of implementing the program at Pennington Biomedical Research Center's TReCC.

Acceptance and feasibility will be assessed by the number of participants enrolled and the number of camp sessions attended. Cybercycling acceptability and enjoyment will be assessed by a survey administered to the child after cybercycling for about 15 minutes.

Endpoints

The primary endpoint is the change in body weight. The secondary endpoints include self-reported changes in health behaviors, quality of life, mood and feelings, self-esteem, weight management efficacy, enjoyment of physical activity, and body image, as well as acceptability/enjoyment of cybercycling.

Procedures Involved

All participants will be explicitly told that their participation is voluntary and that they may terminate their participation at any time.

Consent and Assent Process. Informed consent for the child will be obtained from one of the participant's parents/legally authorized representatives prior to conducting any study procedures. The parent/legally authorized representative will be given an informed consent form to read and sign indicating their permission to allow their child to participate in the study. Parents will return this consent form to the study staff before the child's first visit. Because there is not a greater than minimal risk, informed consent will be obtained from one parent even if the other parent is alive, known, competent, reasonably available, and shares legal responsibility for the care and custody of the child.

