Participants 12 years of age and older will be given a written assent form to read and sign before participating in any study procedures. Participants 6-11 years of age will be read an assent script and asked to verbally assent before participating in any study procedures. Participants 9-11 years of age with a high reading comprehension and maturity level may give written assent, rather than verbal assent, if deemed appropriate by the investigator or research staff member performing the assent. The study procedures will be explained using age appropriate terms, and children will be given the opportunity to ask questions about the study.

Parent survey. Parents will be asked to complete a questionnaire that will provide information on the child's sociodemographic characteristics, including sex, date of birth, and parents' marital status, highest level of education, family income, occupation, and employment status, as well as brief medical history. Parents will report their own height, weight, age, and sex.

Anthropometric measurements. Height and weight of each child will be measured in a private setting with the child dressed in light clothing. Height will be measured to the nearest 1.0 cm using a portable stadiometer. Weight will be measured to the nearest 0.1 kg using high-precision electronic scale. Percent body fat will be recorded from this scale. Body mass index (BMI) z-score will be calculated based on the child's age, sex, height, and weight, then compared to the 2000 Centers for Disease Control and Prevention (CDC) Growth Charts to calculate percentile and z-score.

Surveys. A pre-test and post-test psychosocial questionnaire will be completed by each participant at the beginning (session 1 or orientation) and end (session 5) of the program. The questionnaire will collect information about lifestyle, including diet and physical activity habits, media use, and sleep.

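### Do the unadjusted t-tests and the gender and income models on secondary outcomes need a multiplicity correction?

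*SAP*

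**What the plan says.** The SAP has no section headings. It reports two layers of inference on the same outcomes.

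- First layer: "We used SPSS to conduct paired t-tests to analyze any pre-to-posttest changes in health behaviors and psychosocial well-being outcomes", with Cohen's d as the aid to interpretation.
- Second layer: repeated-measures MANOVAs "by gender (boys vs. girls) and household income", the income groups being divided at $50,000.

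The error rate appears once, at the end of the paragraph: partial eta squared "was reported as effect size from results from the RM-MANOVAs, while significance level was set to be" 0.05. Exploratory wording also appears once: "We further explored the pre-to-posttest changes in the outcomes". It refers to weight status, where the analysts give effect summaries "but did not perform inferential statistical analysis due to the uneven sample sizes between the weight groups".

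The Protocol, under Endpoints, makes body weight primary and continues: "The secondary endpoints include self-reported changes in health behaviors, quality of life, mood and feelings, self-esteem, weight management efficacy", followed by physical activity enjoyment, body image and the cybercycling survey. Under Surveys it says: "The questionnaire will collect information about lifestyle, including diet and physical activity habits, media use, and sleep". Under Number of Subjects: "A total of 12 participants were enrolled in summer 2017 and an additional 50 are anticipated for summer 2018". Under Study Endpoints, feasibility is judged by enrolment and attendance, and weight-related and psychosocial changes are to be interpreted through effect sizes.

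**The concern.** The SAP names classes of outcome, not individual scores, so a reader cannot tell how many p-values were produced. The scales described under Procedures Involved have several subscales each, so the number could be well above ten. Nothing orders the tests. The MANOVAs come after the t-tests and do not gate them. The one analysis described as exploratory is the one without p-values, which could suggest that the others are confirmatory.

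At stake is interpretation. One p-value below 0.05 among many could be read as an effect of the camp on, say, sleep or self-efficacy. A chance interaction could likewise be read as showing that boys and girls, or richer and poorer households, respond differently.

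**Working it through.** **Figure to reproduce.** There is none. Neither document gives a family-wise error rate, a test count or a power calculation. The heading Power analysis in the Protocol describes difference scores and effect sizes only.

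**Inputs.** The per-test level is 0.05 (SAP). The number of tests, k, has to be assumed:

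- k = 3: PedsQL, WEL and PACES, one score each. These are the named scales used in both summers.
- k = 7: those three plus diet, physical activity, media use and sleep. A count of the seven secondary pre-post domains under Endpoints also gives 7, but it is a different set.
- k = 14: four PedsQL domains, five WEL dimensions, PACES and four behaviours.
- k = 24: every score the Protocol supports. That is 4 behaviours, 1 mood, 1 self-esteem, 5 IWQOL-Kids, 6 PedsQL, 5 WEL, 1 PACES and 1 BIA-P.

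The first, second and third lists leave out mood and self-esteem, for which the Protocol names no instrument.

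**Chance of at least one false positive, all nulls true.** For independent tests this is 1 − 0.95^k. The correlated columns come from simulating equicorrelated two-sided z-tests; the correlations are assumed.

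| k | Independent | r = 0.3 | r = 0.5 | r = 0.7 |
|---|---|---|---|---|
| 3 | 14.3% | 13.7% | 12.6% | 10.9% |
| 7 | 30.2% | 27.0% | 22.9% | 17.9% |
| 14 | 51.2% | 43.8% | 34.8% | 25.0% |
| 24 | 70.8% | 59.6% | 45.9% | 31.1% |

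For the subgroup models, one time-by-group test per factor gives 1 − 0.95^2 = 9.8%. If behaviours and psychosocial outcomes were modelled separately, 1 − 0.95^4 = 18.5%. Both assume independence.

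These are probabilities for the whole set. Each single test still has its stated 5% error, and the expected number of false positives is 0.05k: 0.35 for 7 tests, 1.2 for 24.

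**What a correction would cost.** Holm's first step with 7 tests requires p ≤ 0.05/7 = 0.0071. The mean change detectable with 80% power in a paired t-test (noncentral t), in SD of change, becomes:

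| Pairs (assumed) | At 0.05 | At the corrected first step |
|---|---|---|
| 50 | 0.404 | 0.519 (0.05/7) |
| 62 | 0.362 | 0.462 (0.05/7) |
| 12 | 0.889 | 1.269 (0.05/9, with the two 2017-only scales included) |

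For a true change of 0.5 SD at 50 pairs, power falls from 93% to 76% at that first step; for 0.3 SD it falls from 55% to 26%. Later Holm steps are less severe. The 62-pair row assumes that both camps are pooled and the 2018 target is met, so 50 and 62 are favourable values.

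**How precise the estimates are without any p-value.** The 95% confidence interval half-width for a mean change is t/√n in SD of change. For 12 children it is 0.64. IWQOL-Kids is given only from age 11, so 0.64 is a lower bound for that scale: at an assumed 8 children it is 2.365/√8 = 0.84, and at an assumed 6 it is 2.571/√6 = 1.05. For a subgroup difference in mean change with an assumed even split, 25 against 25 gives 0.57 and 31 against 31 gives 0.51. Intervals this wide already discourage firm claims from the small-sample scales and the subgroup models, whether or not p-values are corrected.

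**The case for a change.** The strongest case for a change is that these are the only inferential analyses in the SAP, so a reader has no better-protected result to rely on. Secondary rank tells the reader that a result is not the main claim, but it does not lower the error rate. Even the smallest count considered gives 11% to 14%, at least twice the nominal level. The remedy needs no new data, and adjusted p-values could be printed beside the raw ones.

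The arithmetic stands, and so does the observation that no inferential analysis carries an exploratory label. Some of the rest carries less weight.

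- The 0.05 clause sits in the sentence on the MANOVAs, but in a one-paragraph plan it reads naturally as applying throughout. The t-tests are not left without a level.
- The absence of other inferential analyses reflects the SAP's silence on body weight. That is a separate matter, which adjusting secondary p-values would not repair.
- The SAP is written in the past tense. A correction chosen after the tests were run does not supply prespecified control, and it does nothing about the absence of a comparison group, which limits causal reading far more than multiplicity does.

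**Conclusion.** No change to the plan follows. The inflation is real as a property of the whole set: about 18% to 30% for an assumed 7 tests, and 11% to 71% over the counts and correlations considered. It would matter if the documents claimed that the family was controlled at 5%, or that any significant secondary outcome showed the camp to be effective. They claim neither. The outcomes are secondary, feasibility is judged on enrolment and attendance, and both documents use effect sizes to interpret change. No stated rule yields a wrong result.

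Two kinds of issue remain. The missing list of tests, including whether mood and self-esteem were among them, is a gap that analysts would ordinarily fill when they tabulate results, and secondary tests in a single-arm feasibility study are ordinarily read as exploratory. Whether to adjust is a fair trade-off: protection for the set against a detectable change of 0.52 instead of 0.40 SD at an assumed 50 pairs, with no prespecified control gained.

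This conclusion rests on assumed counts, correlations and numbers of pairs. A larger count would raise both the inflation and the cost of correction, and would not alter the reasoning.

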Weight Efficacy Lifestyle questionnaire (WEL; Summer 2017 and 2018): The WEL assesses self-reported eating habits and perceived self-efficacy in regards to eating and weight loss.⁹ The WEL consists of 20 items designed to measure five hypothetical dimensions of efficacy for weight management: availability, negative emotions, physical discomfort, positive activities, and social pressure. The items were slightly reworded to make them easily understandable to a pre-adolescent population. Good reliability and validity have been reported for the WEL in adult populations^{9,10} and adequate scale reliability in children ($\alpha=0.94$).¹¹

The Physical Activity Enjoyment Scale (PACES; Summer 2017 and 2018): The PACES is a 16-item measure of enjoyment during physical activity.¹²

The Body Image Assessment of Preadolescents (BIA-P; Summer 2017 only): The BIA-P is a reliable and valid measure of body image in children ages 6 to 14.^{13,14}

During summer 2018 camp only, children will be allowed to use the HD Expresso cybercycling stationary bicycles in the TReCC for 15 minutes each. Afterwards, they will complete a brief survey on their enjoyment and acceptability of the cybercycling.

(Summer 2018) One month after the conclusion of the camp, an optional post-camp celebration will be hosted at a local community center for all parents and camp participants. Participants' height and weight will be measured. Participants will be asked to complete a brief survey.

The following is the train schedule for procedures:

	PRE-VISIT	V1 Day 1	V2 Day 5	1 month Post- Visit
Consent	x			
Parent Questionnaire	x			
Assent	x			
Height		x	x	x
Weight		x	x	x
Child Questionnaires		x	x	x

Power analysis.

Difference scores will be calculated between initial and final assessment, and effect sizes will be calculated using linear mixed models to determine clinical significance of weight-related and psychosocial changes throughout the program. Acceptance and feasibility will be assessed by the number of participants enrolled and the number of camp sessions attended.

Data and Specimen Management

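### The SAP estimates survey change only from children with both a pre-test and a post-test; a two-visit mixed model on the larger scales would be a cheap, modest improvement

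*SAP*

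**What the plan says.** The SAP is a single paragraph. For change between the two surveys it says: "We used SPSS to conduct paired t-tests to analyze any pre-to-posttest changes in health behaviors and psychosocial well-being outcomes". It continues that "we conducted repeated measure multivariate analyses of variance (RM-MANOVAs) to examine pre-to-posttest changes in health behaviors and psychosocial well-being outcomes by gender" and household income. Change by weight status is then described without testing, "using gain scores: posttest – pretest data) by weight status (normal weight, overweight, obesity". It gives no rule for missing surveys, no count of incomplete children, and no mention of a mixed model.

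The protocol names a different method for the same outcomes. Under Study Endpoints, Aim 1: "Difference scores will be calculated between initial and final assessment, and effect sizes will be calculated using linear mixed models". The Power analysis section repeats that "effect sizes will be calculated using linear mixed models to determine clinical significance of weight-related and psychosocial changes throughout the program". Neither place gives the visits, the covariance structure or a missing-data assumption.

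Three other protocol provisions bear on this:
- Surveys: "A pre-test and post-test psychosocial questionnaire will be completed by each participant at the beginning (session 1 or orientation) and end (session 5".
- Withdrawal of Subjects: children may leave at any time, and data already collected from them are to be used unless someone requests otherwise.
- Procedures Involved: child questionnaires fall on Day 1, Day 5 and, for 2018 only, at an optional event one month later. IWQOL-Kids and BIA-P were given in summer 2017 only, when 12 children enrolled, and IWQOL-Kids only from age 11. PedsQL, WEL and PACES were given in both summers.

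**The concern.** A paired t-test and a gain score need both values, and RM-MANOVA as normally run also drops incomplete children. A child with a Day 1 survey and no session-5 survey therefore adds nothing to any change estimate in the SAP, and the results describe completers only.

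That matters if absence at session 5 depends on the Day 1 score. If low scorers are the ones missing, those who remain start higher and regress toward the mean, so improvement is understated. If high scorers are missing, it is overstated. Survey change covers most of the secondary endpoints, and the protocol wants effect sizes in order to judge clinical significance, so bias in the estimate matters as well as the p-value.

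Naming a mixed model again would not settle this. A model fitted to difference scores is still completer-only, and a plain random intercept removes the bias only when the two visits have equal variance.

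**Working it through.** **The plan's own figures.** The Power analysis section contains no calculation, and no dropout rate, SD or correlation is given. The only arithmetic to confirm is enrolment: 12 + 50 = 62, which agrees with the stated maximum.

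**Assumed inputs (not in the documents).** Visit correlation rho = 0.7. Ratio of Day 5 SD to Day 1 SD, k = 1. Logit P(Day 5 missing) = a - 1.0 x z, where z is the Day 1 z-score. Loss of 6%, 11% or 22%, which is about 4, 7 or 14 of 62 children.

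**Bias of the paired estimate.** Write the Day 5 score, in Day 1 SD units, as change + k x rho x z + noise, with the noise unrelated to absence. Then

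bias = (k x rho - 1) x E[z | Day 5 present].

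The multiplier is 0.7 - 1 = -0.3. Coverage and SEs come from 20,000 simulated trials per row (n = 62, true change 0.2 SD). RMSE is the square root of bias squared plus SE squared.

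| Loss | a | E[z, Day 5 present] | Paired bias (SD) | Paired 95% CI coverage | SE paired / unstructured | RMSE paired / unstructured |
|---|---|---|---|---|---|---|
| 6% | -3.166 | 0.056 | -0.017 | 94.4% | 0.1015 / 0.1016 | 0.103 / 0.102 |
| 11% | -2.447 | 0.099 | -0.030 | 93.9% | 0.1042 / 0.1046 | 0.108 / 0.105 |
| 22% | -1.510 | 0.189 | -0.057 | 91.7% | 0.1119 / 0.1131 | 0.126 / 0.113 |

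The unstructured two-visit model's bias stayed within 0.002 SD of zero in every row.

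**In points.** On a 0-100 score such as the PedsQL, with an assumed SD of 10 to 20, the bias is 0.3 x E[z] x SD. That gives 0.2-0.3, 0.3-0.6 and 0.6-1.1 points.

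**Sensitivity to the assumptions.**
- Correlation 0.5: multiplier -0.5, bias -0.028, -0.050 and -0.095 SD.
- Half the slope (0.5 per SD) at 22% loss: E[z] = 0.106, bias -0.3 x 0.106 = -0.032 SD, coverage about 94%.
- k = 0.8 at 22% loss: (0.8 x 0.7 - 1) x 0.189 = -0.083 SD for the paired test, -0.027 for a random-intercept model and 0.000 for the unstructured model.
- Body weight, at an assumed correlation of 0.99 and 22% loss: -0.01 x 0.189 = -0.002 SD.

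**Precision if absence is random.** The variance ratio, mixed to paired, is 1 - (1 - rho) x m / 2, where m is the share missing. With 12 of 62 missing (m = 0.194) and rho = 0.3, this is 1 - 0.7 x 0.194 / 2 = 0.932, an SE 3.4% smaller. With rho = 0.8 it is 1.0% smaller. The case therefore rests on bias, with little gain in power.

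**The 12-child scales.** With n = 12 and the same inputs, simulated RMSE at 6%, 11% and 22% loss was 0.234, 0.242 and 0.266 for the unstructured model, against 0.233, 0.239 and 0.260 for the paired estimate. Paired coverage was already about 94.5% to 95%. On these scales the mixed model is slightly worse.

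**The case against.** The strongest reply is that no problem is documented. The programme lasts five daytime sessions, and the protocol expects every child to complete both surveys. Loss, selectivity and correlation above are all assumed. At 6% loss the bias is about a sixth of the standard error (0.017 / 0.1015 = 0.17), and coverage is hardly touched. Paired t-tests are conventional in a single-arm study with two time points, and change among children assessed twice is a legitimate target. The SAP is written in the past tense, so a new main model could look like a choice made after the results.

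Much of this stands. It fixes the rating at minor, and it rules out replacing the paired test on the 12-child scales. It does not remove the point. An expectation of complete surveys is not evidence of it; the protocol itself provides for withdrawal and treats sessions attended as a feasibility measure. Nor is a mixed model a new idea here, since the protocol names one for these outcomes.

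A reader might go further and infer that the SAP breaks a protocol commitment to a visit-level mixed model. The documents do not support that. The protocol mentions difference scores and mixed models in the same sentence and does not say which data the model is fitted to. Likewise, the withdrawal provision does not say that the data must enter a change estimate.

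**Conclusion.** The point holds as a minor design improvement for the secondary survey endpoints. Every change analysis in the SAP is completer-only. If Day 5 surveys are missing in a way that depends on the Day 1 score, the paired mean change for all children assessed on Day 1 is off by roughly 0.02 to 0.06 Day 1 SD over 6% to 22% loss. It reaches 0.08 to 0.10 SD at 22% loss only if the correlation is as low as 0.5 or the Day 5 SD shrinks to 0.8 of Day 1. These sizes rest on assumed loss, selectivity and correlation, on 62 children (a ceiling, of whom 50 were only anticipated), and on absence being explained by the Day 1 score.

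A reader might infer that children were in fact lost and that the survey results are biased. Neither document shows a single missing post-test, and with none missing the two methods give the same mean change. Nor does the point reach the primary endpoint: body weight is too highly correlated over five days, on the assumption used, for selection on the Day 1 value to matter.

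**What to change.** 1. For survey outcomes collected in both summers (e.g. PedsQL, WEL, PACES), estimate Day 5 minus Day 1 with a mixed model on all Day 1 and Day 5 records, including children with Day 1 only. Use visit as a fixed effect, an unstructured 2x2 covariance within child and no extra random intercept, with Kenward-Roger or Satterthwaite degrees of freedom.
2. Leave the optional 2018 one-month visit out of this contrast.
3. Show the paired t-tests alongside, labelled as completer results.
4. For IWQOL-Kids and BIA-P (2017 only, at most 12 children), keep the paired test as the main analysis and use the mixed model only as a sensitivity analysis.
5. For every scale, report how many children lack Day 5 data, and their Day 1 values beside those of the children who have it. This is worth doing in any case, because it tells the reader whether the bias can be more than negligible.

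The cost is a small re-analysis of data already held, with no new collection. The model relies on missing-at-random and does not correct for children whose unmeasured response differed. If few children lack Day 5 data, it gains nothing over the paired test.

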During summer 2017 camp only, children will be asked to complete a friendship nomination survey at the start and end of the 5-day ADA camp. On day 1, each child will be asked whether they know any other child participating in the camp. On day 5, another friendship nomination survey will be completed detailing the friends that the child met during the course of the camp. These friendship nomination data will be used to provide a longitudinal illustration of the ego-centric and overall social network developed during the span of the camp. This friendship nomination method has been used in the National Longitudinal Study of Adolescent Health, a nationally representative study in which one of the primary aims were to measure the association between adolescent social contexts and health and well-being. The survey questions will be from the following validated scales:

Impact of Weight on Quality of Life (IWQOL-Kids) (Summer 2017 only): The IWQOL-Kids is a 27-item measure of weight-related quality of life. Each item begins with the phrase, “Because of my weight,” and contains five response options, ranging from “always true” to “never true.” In addition to a total score, there are scores on four domains: Physical Comfort, Body Esteem, Social Life, and Family Relations. Scores range from 0–100, with higher scores representing better quality of life. The IWQOL-Kids has demonstrated good internal consistency, as well as sensitivity and responsiveness.^{6,7} The IWQOL-Kids will be administered to participants aged 11 and older.

PedsQL (Summer 2017 and 2018): The PedsQL is a general health related quality of life self-report measure with complementary scales for children (ages 6–14).⁸ The measure assesses physical, emotional, social, and school functioning, and provides a psychosocial summary score as well as a total score. Scores range from 0–100, with higher scores representing better quality of life. The PedsQL has been shown to be both reliable and valid in this age range.⁸

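### The gender and income comparisons of change name no age covariate in a sample aged 6 to 14, so an age effect, if there is one, could be read as a gender or income effect

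*SAP*

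**What the plan says.** The SAP first runs paired t-tests on the whole sample. It then uses RM-MANOVAs "to examine pre-to-posttest changes in health behaviors and psychosocial well-being outcomes by gender (boys vs. girls) and household income", dividing income at $50,000 and reporting partial eta squared. On testing it says "significance level was set to be" 0.05. No covariate is named, and it is not stated whether gender and income share a model. On presentation it says: "Descriptive results including both raw and estimated marginal means were obtained to quantify and visualize group differences". It does not say what the marginal means adjust for. Weight-status groups are described without inference.

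The protocol's eligibility criterion is "Aged 6 to 14 years". The parent survey collects "sociodemographic characteristics, including sex, date of birth", so age is available for every child whose parent completes it. On sample size it says: "We plan to enroll up to 62 participants total", made up of 12 in 2017 and 50 anticipated in 2018. The linear mixed models mentioned under Study Endpoints and under Power analysis list no covariates either.

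**The concern.** Boys and girls, and children above and below the income split, are not formed by randomisation, so nothing guarantees similar ages. The age range spans nine year-groups and the outcomes in these models are children's self-reports. Taking each child's change removes any age effect that is constant over the week. It does not remove an age effect on the change itself. If younger and older children respond differently to the camp, and one gender or income group is older, the time-by-group test picks up both effects together.

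These comparisons are tested at 0.05, whereas the weight-status comparison was deliberately left descriptive. A significant result is therefore likely to be attributed to gender or income. At stake is how exploratory comparisons of secondary outcomes are interpreted.

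**Working it through.** The documents give no power figure, SD of change, group sizes, age by group, or age-change correlation, so there is no stated figure to reproduce beyond 12 + 50 = 62.

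**Inputs from the documents:** ages 6 to 14; maximum N of 62; alpha 0.05 (two-sided assumed).

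**Assumed:** whole-year ages spread evenly over 6 to 14; equal groups of 31; within-group correlation r between age and change of 0 to 0.5; a systematic difference in mean age of 1 or 2 years.

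**Reduction to a simple test.** With two time points and a two-level factor, the time-by-group test for one outcome equals a two-sample t-test on gain scores. The multivariate test is not modelled here.

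**Age SD:** sqrt((9² − 1)/12) = 2.58 years.

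**Bias** in SDs of change = (age gap / 2.58) × r. The false-positive rate is the two-sided rejection probability of a noncentral t with 60 df and noncentrality bias / sqrt(1/31 + 1/31) = bias / 0.254. For a 1-year gap and r = 0.3, bias = 0.3/2.58 = 0.116 and noncentrality = 0.457.

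| r | Bias, 1-year gap | False-positive rate | Bias, 2-year gap | False-positive rate |
|---|---|---|---|---|
| 0 | 0 | 5% | 0 | 5% |
| 0.1 | 0.04 SD | 5.3% | 0.08 SD | 6.0% |
| 0.3 | 0.12 SD | 7.4% | 0.23 SD | 14.7% |
| 0.5 | 0.19 SD | 11.7% | 0.39 SD | 32.3% |

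A separate simulation with a 1-year gap gave 7.8% (r = 0.3) and 11.7% (r = 0.5) unadjusted, against 4.9% and 5.4% with age in the model.

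**Precision.** Adding age multiplies the variance of the group difference by about (1 − r²) × (1 + 1/(N − 4)) and costs one degree of freedom per outcome. At N = 62 and r = 0 the factor is 1 + 1/58 = 1.017, so the standard error rises by 0.9%.

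| r (N = 62) | Change in standard error | Power for a 0.5 SD difference (49.1% unadjusted) |
|---|---|---|
| 0 | +0.9% | 48.4% |
| 0.1 | +0.4% | 48.8% |
| 0.2 | −1.2% | 50.0% |
| 0.3 | −3.8% | 52.1% |
| 0.5 | −12.7% | 60.1% |

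Setting the factor to 1 gives the break-even r² = 1/(N − 3). That is |r| = 0.13 at N = 62, 0.15 at N = 50 and 0.33 at N = 12.

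**Marginal means.** With one grouping factor and no covariate, they equal the raw means of the complete cases. With gender and income crossed, they weight the cells equally. The SAP does not say which applies, or whether an unreported covariate was used.

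**The case against.** The strongest reply is that nothing in the documents shows a problem. No table gives age by gender or income, and nothing links age to one-week change. Without both, the bias is zero, and at r = 0.1 a 1-year gap is negligible. The comparisons appear in no aim or endpoint, and an unadjusted contrast is a legitimate description. All of this stands, and it limits the point to a possible confounder in exploratory analyses. It does not remove the point: the comparisons are formal tests, differencing does not cancel age-related change, and no other section adjusts for age.

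Four stronger readings are tempting and are not supported:

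- **That the protocol itself shows change to depend on age.** It says "The IWQOL-Kids will be administered to participants aged 11 and older", and the WEL items were reworded for pre-adolescents. Both concern whether an instrument suits a child, or the level of response, not one-week change. IWQOL-Kids was also used only in 2017, with at most 12 children.
- **That chance imbalance inflates error.** A gap of 1 year or more arises by chance in about 13% of samples (standard error of the gap 2.58 × sqrt(2/31) = 0.66 years). The unadjusted test already allows for this. If age is independent of group, it rejects 5% of the time overall whatever r is. The rates in the table require a systematic gap.
- **That adjustment is free precision.** It loses slightly below the break-even r and gains little up to 0.3.
- **That the marginal means adjust for nothing.** The SAP is silent, so the supportable point is a reporting gap.

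**Conclusion.** The concern holds as a gap in the SAP: two non-randomised groupings are tested with no age adjustment stated, although the age range is wide and date of birth is collected. It does not establish that any reported gender or income difference is due to age. Under the assumed age SD and 31 v 31 split, a systematic 1-year gap moves the false-positive rate from 5% to between about 5.3% and 11.7% as r goes from 0.1 to 0.5. With no gap or no age-change link, there is no effect. N = 62 is a ceiling, so actual group sizes may be smaller. The whole-sample paired t-tests are unaffected because each child is their own control, and the primary weight endpoint is not among the outcomes of these models.

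**What to change.** 1. Tabulate age at Day 1 by gender and by income group.
2. For outcomes collected in both summers, report beside the unadjusted RM-MANOVA results an analysis that adds Day 1 age, centred at the sample mean, and its interaction with time. Centring keeps the time effect interpretable.
3. Label it a sensitivity analysis. The SAP is written in the past tense about completed work, so replacing the model now would be a post-hoc change.
4. State what the estimated marginal means adjust for, and whether gender and income share a model.
5. Do not apply the adjustment to scales used only in 2017 (IWQOL-Kids, BIA-P). With at most 12 children it would lose precision unless |r| exceeded about 0.33.

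The cost is one extra model term, one degree of freedom per outcome, and about 0.9% on the standard error at N = 62 if age is irrelevant. No new data are needed.
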